12. INTERIM ANALYSIS

There is no interim analysis of efficacy planned for this study.

13. CHANGE FROM ANALYSIS PLANNED IN PROTOCOL

The raw values for the following endpoints will be included in data listings, but the change values will not be listed or summarized:

- Secondary safety endpoints
 - Change in PEF
 - Change in C-ACT and ACT score
 - Change in TNSS
- Secondary efficacy endpoints:
 - Change in tolerated dose of peanut protein
 - Changes in food allergy QoL scores as measured by FAQLQ and the FAIM questionnaire
 - Change in FAQL-PB questionnaire score
- Exploratory endpoint:
 - Change in TRACK and EASI scores

Real world peanut challenge results will be presented in data listings and used to identify TEAEs. An analysis of these data was described in a previous version of the protocol (Protocol amendment 3 / Appendix 8).

14. **REFERENCE LIST**

DunnGalvin A, de BlokFlokstra BM, Burks AW, Dubois AE, Hourihane JO. Food allergy QoL questionnaire for children aged 0-12 years: content, construct, and cross-cultural validity. Clin Exp Allergy. 2008;38(6):977-86.

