1.3 Rationale for the Current Study

ARC008 is an open-label, international, longer-term extension study for eligible subjects who participated in prior or future Aimmune AR101 clinical studies. The rationale for conducting ARC008 is as follows:

- To allow subjects who received placebo in Aimmune-sponsored clinical studies with AR101 to receive AR101 drug product
- To allow subjects who received AR101 in Aimmune-sponsored clinical studies to continue treatment
- To assess safety and tolerability during longer-term administration of AR101 and follow-up observation after the last dose of AR101
- To explore whether the level of desensitization to peanut protein is maintained or continues to increase after longer-term administration of AR101 and follow-up observation after the last dose of AR101

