9.1 Sample Size

There is no sample size calculation for this study. The sample size will be determined by the number of eligible subjects from each of the prior AR101 studies who participate in this study.

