9.2 Analysis Conventions

Data will be summarized using descriptive statistics. No specific hypothesis testing or comparisons are planned for this study.

Continuous data (ie, age, body weight, and height) will be summarized descriptively using mean, standard deviation, median, and range. Categorical data (ie, sex and race) will be presented as enumerations and percentages.

Data will be listed for each subject.

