9.6 Efficacy Analyses

All efficacy endpoints will be summarized using descriptive statistics. Further details will be provided in the SAP.

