9.7 Safety Analyses

All safety endpoints will be summarized using descriptive statistics. Further details will be provided in the SAP.

AEs will be coded based on the Medical Dictionary for Regulatory Activities terminology. Events will be tabulated by system organ classification and preferred term.

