2.2. SECONDARY OBJECTIVES

The secondary objectives of the study are to:

- Assess the level of desensitization achievable through extended maintenance dosing of AR101
- Characterize the interaction of AR101 and asthma control or nasal allergy symptoms in subjects with a history of asthma and/or allergic rhinitis
- Evaluate subjects' quality of life (QoL) and treatment satisfaction during AR101 treatment on daily and non-daily treatment regimens
- Evaluate parent/caregiver QoL during the child's treatment with AR101

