6.5. SIGNIFICANCE LEVEL

No formal statistical analysis will be performed. This study is exploratory in nature; descriptive statistics will be tabulated and reviewed to evaluate all study endpoints.

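### SAP Section 13 drops the change summaries for six of ten secondary endpoints without a stated reason, leaving three of four secondary objectives with no planned summary of their endpoints

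*SAP*

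**What the plan says.** The protocol makes two general commitments. Section 9.6 says "All efficacy endpoints will be summarized using descriptive statistics" and Section 9.7 says "All safety endpoints will be summarized using descriptive statistics"; both leave further detail to the SAP. SAP Section 6.5 repeats the commitment: "descriptive statistics will be tabulated and reviewed to evaluate all study endpoints". SAP Sections 3.1 to 3.3 still carry every change endpoint.

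SAP Section 13 then lists seven items whose raw values "will be included in data listings, but the change values will not be listed or summarized". Three are secondary safety endpoints (PEF, C-ACT/ACT, TNSS). Three are secondary efficacy endpoints (tolerated dose, FAQLQ with FAIM, FAQL-PB). One is exploratory (TRACK with EASI). No reason is given.

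SAP Section 2.2 keeps all four secondary objectives. One of them is: "Characterize the interaction of AR101 and asthma control or nasal allergy symptoms in subjects with a history of asthma and/or allergic rhinitis". Another is to evaluate subjects' quality of life on daily and non-daily regimens, and a third concerns caregiver quality of life. Protocol Section 1.3 also gives this reason for running the study: "To explore whether the level of desensitization to peanut protein is maintained or continues to increase after longer-term administration of AR101".

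**The concern.** An objective to characterize asthma control or evaluate quality of life needs at least a descriptive summary. A listing sorted by pathway, subject and visit, in a study that may enrol about 950 subjects, gives the reader no mean, no spread and no trend. The exploratory skin prick test and immunoglobulin endpoints keep their change summaries (SAP Sections 11.1 and 11.2), so several secondary endpoints receive less analysis than exploratory ones, with no explanation.

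For tolerated dose, the question is whether the tables that remain can show desensitization being maintained or rising within a subject. Yearly open-label food challenges (OLFCs) are optional for Pathways 1 to 3, and optional for Pathways 4 and 5 after the first Extended Maintenance year. The subjects behind each yearly rate can therefore change, and a rising rate may partly reflect who chose to be challenged.

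**Working it through.** There is no power or precision figure to reproduce: "There is no sample size calculation for this study" (protocol Section 9.1) and "Data will be summarized using descriptive statistics. No specific hypothesis testing or comparisons are planned for this study" (Section 9.2). The check is a count of endpoints and a comparison of sections.

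**Step 1. Denominators, counting bullets as the SAP groups them.** Section 3.1 has 3 secondary safety endpoints and Section 3.2 has 7 secondary efficacy endpoints: 3 + 7 = 10 secondary. Section 3.3 has 4 exploratory endpoints.

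**Step 2. Each Section 13 item against its analysis section.**

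| Item | SAP section | Planned output |
|---|---|---|
| PEF | 9.7 | Listing only |
| C-ACT/ACT | 9.8 | Listing only |
| TNSS | 9.10 | Listing only |
| FAQLQ, FAIM | 10.3 | Listing only |
| FAQL-PB | 10.3 | Listing of raw scores only, although total and domain scores are derived |
| Tolerated dose | 10.1 | Counts and percentages at each maximum tolerated dose (MTD); response rates with exact 95% CIs; no within-subject change |
| TRACK, EASI (exploratory) | 11.3 | Listing only |

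**Step 3. Counts.** Change summaries dropped: 3 + 3 = 6 of 10 secondary, and 1 of 4 exploratory. Tolerated dose keeps a summary of its level, so 6 − 1 = 5 of 10 secondary endpoints lose every summary through Section 13.

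**Step 4. Objectives.** The asthma and nasal objective rests on PEF, C-ACT/ACT and TNSS. The subject quality-of-life objective rests on FAQLQ and FAIM. The caregiver objective rests on FAQL-PB. All are listing-only, so 3 of 4 objectives have no planned endpoint summary. The fourth, the level of desensitization achievable, is served by Section 10.1. The daily and non-daily subgroups in Section 6.3 apply only to the overall adverse event summary and to rescue medication, so the regimen element of the quality-of-life objective has no output either.

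**Step 5. Can change be computed?** Section 7.4 defines baseline (last non-missing value before the first AR101 dose in ARC008) and change from it. Under that definition Pathways 1, 2 and 4 start from a treated baseline and Pathways 3 and 5 from an untreated one. Section 6.1 generally combines pathways in tables, which would mix two different quantities here.

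**Step 6. Can MTD be paired?** Extended Maintenance OLFCs test 300, 600, 1000 and 2000 mg. The double-blind, placebo-controlled food challenge (DBPCFC) tests eight doses from 3 mg to 2000 mg (protocol Sections 6.2.2 and 6.2.3). The two ladders agree only from 300 mg upward. ARC007 had no food challenges (protocol Section 1.2.3), so subjects who entered directly from it have no parent-study challenge to pair with.

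**The case against.** The cut is declared in the place meant for such changes. SAP Section 1.1 says Version 1 was approved before database lock and that Version 2 changes are confined to Appendix A. The protocol leaves detail to the SAP, sets no endpoint hierarchy and plans no tests. The Section 6.5 sentence is general text under a heading on significance level, and a specific exception can be read as qualifying it. All of this answers any suggestion of concealment. It does not supply a reason, align the two SAP sections, or give the three objectives a summary.

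On tolerated dose the other side is stronger. The stated objective concerns the level of desensitization, which Section 10.1 tabulates. Whether that level is maintained or increases is a rationale item in the protocol, worded as exploration. The End of Treatment DBPCFC is not voluntary: it is planned for all subjects except those who stop early for safety reasons or who have oat or rice allergy. OLFCs are required at Month 12 of Extended Maintenance for Pathways 4 and 5, and at the end of Initial Maintenance for Pathway 5. Rescue medication at challenges is also tabulated (Section 9.12). What remains of the concern is that no paired, within-subject comparison is planned.

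The data may also not be fully clean. SAP Section 7.7 reports that some locked or frozen data had to be adjudicated because the study ended early. That calls for a note on the tables. It is no reason to omit them, since the same values are to be listed.

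**Conclusion.** The point stands and should be corrected. Section 13 removes the change summaries for 6 of 10 secondary and 1 of 4 exploratory endpoints. Five secondary items and TRACK/EASI are left with listings only, and 3 of 4 secondary objectives have no planned endpoint summary, contrary to protocol Sections 9.6 and 9.7 and SAP Section 6.5. The counts take each SAP bullet as one endpoint.

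A reader might infer more than the documents support:

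- That six secondary endpoints lose all summaries. Tolerated dose does not.
- That desensitization goes unanswered, or rests only on self-selected volunteers. Section 10.1 and the End of Treatment DBPCFC contradict both.
- That the three other objectives cannot be answered at all. Raw values by subject are to be listed; what is missing is a planned summary.
- That the cut followed sight of the final data. The version history in SAP Section 1.1 gives no support for this.

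**What to change.** - Add descriptive tables of observed value and change from ARC008 baseline, by visit, for PEF, ACT, C-ACT, TNSS, FAQLQ, FAIM, FAQL-PB, TRACK and EASI.
- Show Pathways 1, 2 and 4 separately from Pathways 3 and 5. Not every instrument is used in every pathway; FAQL-PB, for example, is collected only in Pathways 3 and 5.
- Show subject quality of life also by daily and non-daily regimen. Under protocol Section 3.1 non-daily subjects enter through Pathway 1, so this comparison belongs within the treated-baseline group.
- Compute no change across different instruments, such as C-ACT to ACT or TRACK to C-ACT as a child ages.
- Add a paired MTD shift table in subjects with two challenges, for example first to last Extended Maintenance OLFC. Limit any OLFC-to-DBPCFC or parent-study comparison to subjects who had both, and collapse MTDs below 300 mg. State the number of pairs: the subset remains selected where the OLFC was optional.
- Label tables added after database lock as post hoc and exploratory, as SAP Section 6.1 requires.

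If the tables are not added, the study report should give the reason, correct the Section 6.5 statement, and name the objectives that were not evaluated.

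The cost is a modest number of descriptive tables: nine instruments, regimen repeats for FAQLQ and FAIM, and the MTD shift table. No new data and no hypothesis tests are needed.

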15. PROGRAMMING CONSIDERATIONS

All tables, data listings and figures (TLFs) will be generated using SAS® for Windows, Release 9.4 or higher (SAS® Institute Inc., Cary, NC, USA).

Report summaries will be generated using validated Base SAS[®] software, version 9.4 or higher, on a server-based platform. Additional validated software may be used to generate analyses, as needed.

Data will be analyzed by Precision for Medicine personnel. Statistical analyses will be reported with tables, listings and figures, presented in both rich text and pdf format, and using recommended ICH numbering. Output specifications for all tables, figures and listings will be in conformance with guidelines specified by the ICH in Appendix 7 of the *Electronic Common Technical Document Specification* (2008).

16. QUALITY CONTROL

All SAS programs that create outputs or supporting analysis datasets will be validated by a second statistical programmer. At a minimum, validation of programs will consist of a review of the program log, review of output or dataset format and structure, and independent confirmatory programming to verify output results or dataset content. Additionally, all outputs will undergo a review by a senior level team member who is also an appropriately qualified statistician before finalization.

The content of the source data will be reviewed on an ongoing basis by statistical programmers and statisticians. Data will be checked for missing values, invalid records, and extreme outliers through defensive programming applications, analysis-based edit checks, and other programmatic testing procedures. All findings will be forwarded to data management for appropriate action and resolution.

17. STUDY SCHEDULE

Refer to the protocol for the full study schedule of events (Appendices 1-6).

18. INDEX OF TABLES, LISTINGS AND FIGURES

An index of the planned statistical outputs will be provided in the shell TLF document.
